4.2.6.4 Vital signs, weight and BMI

Baseline and post-baseline vital signs, weight and BMI will be summarized descriptively by visit. Change from baseline at each visit will also be summarized. Box plots of the vital signs results by visit will be presented.

All baseline and post-baseline vital signs, weight and BMI will be listed.

4.2.6.5 Physical examinations

Patient with PE in the study will be listed.

4.2.6.6 ECGs

The change from baseline ECG evaluation to post-baseline ECG evaluation will be summarized using shift table. The worst case will be used as post-baseline result for analysis. Only when there is no post-baseline clinical evaluation, the worst post-baseline of ECG evaluation will be considered as unchecked in shift table.

Patient with abnormal ECG results in the study will be listed.

4.2.6.7 ECOG PS

A summary of ECOG performance status at each scheduled time point will be provided.

ECOG PS in the study will be listed.

4.2.6.8 Pregnancy test

Patients with positive baseline or post-baseline pregnancy test results will be listed.

4.2.6.9 Potential Hy's Law case

Liver diagnosis, liver risk factors and liver signs and symptoms regarding PHL case will be listed by patient and PHL case.

4.2.7 Subsequent anti-cancer therapy

Subsequent anti-cancer therapy is the anti-cancer therapy which start after the last dose of study drug. Variables of subsequent anti-cancer therapy will include no. of patients with anticancer therapy post IP, therapy class, therapy agent and no. of cycles. These variables will be summarized using descriptive statistics for continuous and categorical variable accordingly.

4.2.8 Subgroup analysis

Subgroup analysis of safety and efficacy (i.e. primary and secondary endpoints) will be conducted for the cohorts of patients with PS 0, 1, and 2 at baseline. For time to event analysis, each subgroup must have at least 20 events per subgroup level in order for that subgroup level to be included in the subgroup analysis.

Additional subgroup analyses may be conducted for primary and/or secondary endpoints based on the following:

- Platinum therapy administered in cycle 1 (cisplatin vs carboplatin)
- Sex (male versus female)
- Age (<65 versus ≥65 years of age)
- Smoking status (current and former versus never smoker)
- Number of cycles of EP (≤4 versus >4, based on etoposide exposure)
- Use of PCI (yes versus no)
- Brain metastases (yes versus no)
- Liver metastases (yes versus no)
- AJCC stage (stage III versus stage IV)

Patients with missing data for a subgroup variable will be excluded from the analysis for that subgroup only.

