1.3 Number of patients

This is a safety study and no formal sample size calculation will be done. However, assuming AE of CTCAE grade ≥ 3 with an incidence of 60%, approximately 300 patients are needed to achieve the estimation precision no wider than 5.7% based on exact method (Clopper-Pearson). In addition, assuming the imAE with an incidence of 20%, the estimation precision will be no wider than 4.7% using the same method. An illustration of the precision around the varying incidences of AE for the patients enrolled is provided in Table 1 Precision around varying incidence of AE.

Table 1 Precision around varying incidence of AE

Sample Size	Precision achieved with different assumed incidence of AE				
	20%	40%	50%	60%	70%
200	5.8%	7.0%	7.1%	7.0%	6.6%
300	4.7%	5.7%	5.8%	5.7%	5.3%
500	3.6%	4.4%	4.5%	4.4%	4.1%

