4.2.5 Secondary endpoints

4.2.5.1 PFS

PFS will be summarized using Kaplan-Meier estimates of the median event time and quartiles together with their 95% CIs, given the anticipated maturity of 60%. The Kaplan-Meier curves will be provided. The no. and proportion of cases of events (e.g. PD, death) and censorings will be summarized.

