5 INTERIM ANALYSES

There will be no formal interim analysis in this study.

As the safety of durvalumab + EP has not been previously established in ES-SCLC patients with PS2, a safety review committee (SRC) will be established to review the safety and tolerability data of the combination of durvalumab+EP in this subset of patients at an early stage of enrolment. SRC will include AZ local study team member such as study physician, PV physician, PM and local medical affairs Lead, and also global clinical lead, global patient safety physician and GMAL.

The SRC will meet after the first 20 patients with PS2 have either had the opportunity to complete the combination of durvalumab + chemotherapy (maximum of 6 cycles) or have discontinued treatment with durvalumab due to an AE or disease progression, whichever occurs first.

After review of the data in patients with PS2, and patients with PS0-1, the SRC will make a recommendation on whether the study should continue recruitment of patients with PS2 as planned, or hold recruitment of this patient population, or amend the study design. In the event that the SRC recommends a change to the study, this will be communicated to all sites.

The primary analysis of the study will be conducted 6 months after LSI, at which time secondary endpoints will also be assessed (maturity for PFS is anticipated to be approximately 60%).

Additionally, final analysis will be performed at the end of the study when all patients have completed follow-up for safety or sufficient maturity for the secondary efficacy objectives has been reached.

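### The 20-event minimum in SAP Section 4.2.8 also covers the mandatory PS cohorts, so PS2 time-to-event summaries can be omitted if that cohort is small

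*SAP*

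**What the plan says.** Section 4.2.8 opens with the PS analysis of the primary and secondary endpoints, which "will be conducted for the cohorts of patients with PS 0, 1, and 2 at baseline". The next sentence of the same paragraph sets the threshold for time-to-event analyses: "each subgroup must have at least 20 events per subgroup level in order for that subgroup level to be included in the subgroup analysis". The other subgroups (platinum agent, sex, age and so on) come only after that, and they are optional: "Additional subgroup analyses may be conducted for primary and/or secondary endpoints based on the following".

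The threshold is confined to time-to-event analyses. In this SAP these are:
- PFS and OS (Sections 4.2.5.1 and 4.2.5.5), and DoR where a Kaplan-Meier analysis is appropriate (Section 4.2.5.4);
- APF12 and OS12, which Sections 3.2.4 and 3.2.8 define as Kaplan-Meier estimates at 12 months;
- time to first grade ≥3 AE and, by the same method, first imAE (Section 4.2.4), with similar analyses for the other AE classes (Section 4.2.5.7).

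Section 5 explains the interest in PS2 when it sets up the safety review committee: "As the safety of durvalumab + EP has not been previously established in ES-SCLC patients with PS2".

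**The concern.** The PS analysis is the one subgroup analysis that the SAP commits to, yet its time-to-event part depends on an event count that the cohort may not reach. The order of the sentences gives no ground for reading the threshold as limited to the optional subgroups.

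The study is single-arm, and Section 4.1.3 calls the primary endpoints descriptive and plans no test of them. The planned PFS and OS medians and quartiles and the 12-month estimates already come with confidence intervals, so imprecision would be visible without leaving anything out. The SAP also treats the same patients in two ways. A PS2 incidence is reported with an exact interval at any cohort size, while a PS2 Kaplan-Meier estimate is dropped below 20 events.

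The rule depends on the outcome as well. Few events, including few because patients did well, lead to omission, and the same cohort could appear for PFS but not for OS. At stake is the PS2 part of the time-to-event efficacy results, in a trial whose efficacy objective covers PS 0-2. If PS2 fell short on PFS, OS and DoR, ORR would be the only secondary efficacy endpoint reported for it.

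**Working it through.** **Inputs from the SAP.** Threshold of 20 events (Section 4.2.8). Total of about 300 patients, assumed grade ≥3 AE incidence 60% and assumed imAE incidence 20% (Section 1.3). Anticipated PFS maturity of about 60% at the primary analysis, six months after LSI (Sections 4.2.5.1 and 5).

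**Inputs assumed.** The SAP gives no PS2 total, so a range of cohort sizes is used. The overall proportions are applied to PS2. Proportions of 40% (a less mature endpoint, such as OS or DoR might be) and 80% (a more mature PS2 cohort) are added to show the range.

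**The plan's own figures.** The threshold has no derivation to reproduce. The precision figures in Section 1.3 do reproduce: with 300 patients, half the width of the exact Clopper-Pearson 95% interval is 5.69% at 60% incidence and 4.68% at 20%, against 5.7% and 4.7% stated. All 15 cells of Table 1 agree.

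**Step 1: cohort size for 20 expected events**, n = 20/p.
- p = 0.6: 20/0.6 = 33.3, so 34 patients, and 34/300 = 11.3% of the trial.
- p = 0.2: 20/0.2 = 100 patients, and 100/300 = 33.3% of the trial.

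**Step 2: chance of reaching the threshold**, P(X ≥ 20) with X binomial(n, p).

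| PS2 patients | p = 0.2 | p = 0.4 | p = 0.6 | p = 0.8 |
|---|---|---|---|---|
| 20 | about 0 | about 0 | about 0 | 0.01 |
| 30 | about 0 | 0.003 | 0.29 | 0.97 |
| 34 | about 0 | 0.02 | 0.63 | 1.00 |
| 40 | about 0 | 0.13 | 0.93 | 1.00 |
| 60 | 0.01 | 0.88 | 1.00 | 1.00 |
| 100 | 0.54 | 1.00 | 1.00 | 1.00 |

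For at least an 80% chance of 20 events, the cohort must have 37 patients at p = 0.6, 57 at p = 0.4 and 116 at p = 0.2.

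**Step 3: what is reported regardless.** Incidences are proportions, so the threshold does not reach them. With 30 PS2 patients and 18 having a grade ≥3 AE, the report would give 18/30 = 60% with an exact 95% interval of 40.6% to 77.3%.

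**The case against.** The strongest reply is that little of importance is lost.

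- **Safety.** A reader might infer that the rule hides PS2 safety results. The SAP does not support that. The primary endpoints are numbers and proportions of patients (Section 3.1) with exact intervals (Section 4.2.4), and the other AE incidences are proportions too. AEs and deaths are listed. The committee's review of PS2 safety in Section 5 carries no event threshold. Only the time-to-first-AE analyses are exposed. This stands in full.
- **Likelihood.** A reader might also infer that omission is certain, or that the lack of a PS2 total is itself a fault. Neither follows. Section 5 refers to recruiting PS2 patients as planned, and the planned number may well stand in the protocol, which is not at hand. This stands.
- **Maturity.** The 60% is an all-patient figure. If PS2 recruitment were held early, those patients would have longer follow-up and probably higher maturity, and the final analysis may add events. Nor does Section 5 say that recruitment stops at 20 PS2 patients. The committee meets once the first 20 have had the opportunity to complete the combination or have discontinued durvalumab because of an AE or progression, and no pause is stated in the meantime. This stands, although a cohort of 20 would very probably miss the threshold even at 80% maturity (0.01).
- **imAE.** At about 20% incidence the Kaplan-Meier median would usually be inestimable even in all 300 patients, so what is lost is mainly a curve. This stands.
- **Reporting choice.** A prespecified minimum that avoids uninformative medians is legitimate. For optional subgroups that is a fair defence. It is weaker for the one analysis that the SAP makes mandatory, where leaving results out conflicts with the commitment to report them.

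**Conclusion.** The point holds in a limited form. As worded, the 20-event minimum applies to the PS 0, 1 and 2 cohorts, and it can remove PS2 Kaplan-Meier summaries. It does not touch PS2 incidences of AEs and imAEs, ORR or the committee's safety review.

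If 60% applied in PS2, omission of PFS or of time to first grade ≥3 AE would be more likely than not at 30 patients (1 − 0.29 = 0.71) and unlikely at 40 (1 − 0.93 = 0.07). At 80% maturity it would be unlikely already at 30 (1 − 0.97 = 0.03). A less mature endpoint needs a larger cohort, and time to first imAE would very probably be omitted at 60 patients or fewer.

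These figures rest on assumed cohort sizes, on overall proportions carried over to PS2, and on independent patients with a common event probability. PS2 rates may differ. The point concerns completeness of reporting. It does not bear on the validity of the primary analysis. It is still worth settling before database lock, because the correction is small and otherwise the event count decides whether a promised result appears.

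**What to change.** Add a sentence to Section 4.2.8, for example: *The 20-event minimum does not apply to the PS 0, 1 and 2 cohorts. Kaplan-Meier estimates with number of events, numbers at risk and 95% confidence intervals are presented for each PS cohort and flagged as imprecise where there are fewer than 20 events.* Keep the minimum for the optional subgroups and say that it applies to those only.

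The cost is one sentence and a footnote in the table shells. The drawback is that small cohorts will show wide intervals or medians that cannot be estimated, which the flag makes plain to the reader.

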3.2.3 PFS

PFS is defined as the time from first dose of study treatment until the date of objective disease progression or death (by any cause in the absence of progression) regardless of whether the patient withdraws from study therapy or receives another anti-cancer therapy prior to progression. Patients who have not progressed or died at the time of analysis will be censored at the time of the latest date of tumor assessment. However, if the patient progresses or dies after 2 or more missed visits, the patient will be censored at the time of the latest assessment. If the patient has no evaluable visits or does not have baseline data, they will be censored at the day of first dose unless they die within 2 visits of baseline (2 x 6 weeks for tumor assessments + 2 x 2 weeks for permitted visit window).

The PFS time will always be derived based on assessment dates not visit dates.

$PFS \text{ (months)} = (\text{Date of event or censoring} - \text{Date of first dose} + 1) / 30.4375$, results round to 1 decimal place. The cases of event and censoring are listed in Table 4 PFS calculation under various cases.

Given the scheduled visit assessment scheme (ie, q6w ± 2w for the first 12 weeks then q8w ± 2w thereafter) the definition of 2 missed visits will change. To evaluate the no. of missing tumor assessments between the first PD/death and the last non-missing tumor assessment before, following rules will be used.

Table 3 Criteria of at least 2 missing tumor assessments

Cases	Conditions when considered as at least 2 missing tumor assessments
There is 2 consecutive missed tumor assessments before first PD/death since first dose.	Time interval between first dose and first PD/death is >16 weeks (ie. 2 * 6 + 4 weeks, 112 days)
If the 2 consecutive missed tumor assessments occur over the period(Week 12) when the scheduled assessments changes from q6w to q8w	Time interval between the last tumor assessment and first PD/death is >18 weeks (ie. 6 + 8 + 4 weeks, 126 days)
If the 2 consecutive missed tumor assessments occur after Week 12 onwards	Time interval between the last tumor assessment and first PD/death is >20 weeks (ie. 2 * 8 + 4 weeks, 140 days)

Table 4 PFS calculation under various cases

Cases	Date used as the end of PFS	Event or Censoring
Patients with PD or death, and first PD or death are within 2 assessments after last tumor assessment before PD/death	Date of first PD or death	Event

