3.2.6 DoR

Duration of response is only calculated for patients who have a best overall tumor response of CR or PR before further anti-cancer therapy after first dose.

Duration of response will be defined as the time from the date of first documented response until the date of PD or death in the absence of disease progression. The end of response should coincide with the date of PD or death from any cause used for the PFS endpoint. The time of the initial response will be defined as the date of tumor assessment for the first response of PR or CR.

If a patient does not progress following a response, then his/her duration of response will use the PFS censoring time.

DoR (months) = (Date of event or censoring – Date of first documented CR or PR before further anti-cancer therapy after first dose + 1) /30.4375, results round to 1 decimal place.

3.2.7 OS

Overall survival is defined as the time from the date of first dose of study treatment until death due to any cause. Any patient not known to have died at the time of analysis will be censored based on the last recorded date on which the patient was known to be alive. The possible last recorded date could be found from visits, AEs, concomitant medication, cancer therapy, vital signs, physical examination, lab test, study drug exposure, survival status survey and disposition of patient.

OS (months) = (Date of death or last recorded date on which the patient was known to be alive - date of first dose of study treatment + 1) /30.4375, results round to 1 decimal place.

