8 APPENDIX

Appendix A Schedule of assessments

Visit	Screening	Treatment period			Safety follow-up visit	Survival follow-up phone calls/emails
		Baseline (Day1)	During Chemotherapy 1 cycle = 21 days	Post-Chemotherapy 1 cycle = 28 days		
Visit window	Day-28 to Day-1	0	±3 days	±3 days	±7 days	±14 days
Week	Weeks-4 to Week-1	Week 0	Week 3, 6, 9; Weeks 12, 15 at investigator discretion	3 weeks after last dose of chemotherapy (either Week 12, 15 or 18), then every 4 weeks until PD	90 days after last dose	Every 3 months
Written informed consent ^a	X					
Inclusion/exclusion criteria	X					
Demographics, including baseline characteristics	X					
Medical history, including cancer treatment history	X					

Visit	Screening	Treatment period			Safety follow-up visit	Survival follow-up phone calls/emails
		Baseline (Day1)	During Chemotherapy 1 cycle = 21 days	Post-Chemotherapy 1 cycle = 28 days		
Visit window	Day-28 to Day-1	0	±3 days	±3 days	±7 days	±14 days
Week	Weeks-4 to Week-1	Week 0	Week 3, 6, 9; Weeks 12, 15 at investigator discretion	3 weeks after last dose of chemotherapy (either Week 12, 15 or 18), then every 4 weeks until PD	90 days after last dose	Every 3 months
ECG recording ^b	X	As clinically indicated				
Physical examination, weight, and vital signs	X	X	X	X	X	
Concomitant medications	X	X	X	X	X	
Laboratory Assessments						
Clinical chemistry ^c	X	X ^d	X	X	X	
Hematology ^c	X	X ^d	X	X	X	
TSH, (reflex free T3 or free T4 ^f)	X	X ^e	X	X	X	
Hepatitis B, C, HIV virology	X					
Pregnancy test ^g	X	X	X	X	X	
Urinalysis	X	As clinically indicated				
Monitoring						
AE	X	X	X	X	X	
ECOG performance status	X	X	X	X	X	
IP Administration						
Durvalumab ^h		X	X	X		
Etoposide ⁱ		X	X ^k			
Carboplatin or cisplatin ^{ij}		X	X ^k			

Visit	Screening	Treatment period			Safety follow-up visit	Survival follow-up phone calls/emails
		Baseline (Day1)	During Chemotherapy 1 cycle = 21 days	Post-Chemotherapy 1 cycle = 28 days		
Visit window	Day-28 to Day-1	0	±3 days	±3 days	±7 days	±14 days
Week	Weeks-4 to Week-1	Week 0	Week 3, 6, 9; Weeks 12, 15 at investigator discretion	3 weeks after last dose of chemotherapy (either Week 12, 15 or 18), then every 4 weeks until PD	90 days after last dose	Every 3 months
Tumor assessment per Investigator - report (according to RECIST1.1) ^l	X	On study tumor assessments should occur at Week 6±2 weeks, at Week 12±2 weeks then every 8±2 weeks ^m until PD				
Subsequent anticancer therapy					X	X
Survival status					X	X

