- a. Written informed consent and any locally required privacy act document authorization must be obtained prior to performing any protocol-specific procedures, including screening/baseline evaluations. If laboratory or imaging procedures were performed for alternate reasons prior to signing consent, these can be used for screening purposes with consent of the patient. However, all screening laboratory and imaging results must have been obtained within 28 days of first dose.
- b. Any clinically significant abnormalities detected require triplicate ECG results.
- c. Serum or plasma clinical chemistry (including LFT monitoring) and hematology may be performed more frequently if clinically indicated.
- d. If screening laboratory assessments are performed within 3 days prior to Day 1 (first infusion day), they do not need to be repeated at day 1.
- e. If TSH is measured within 14 days prior to Day 1 (first infusion day), it does not need to be repeated at Day 1.
- f. Free T3 or free T4 will only be measured if TSH is abnormal or if there is clinical suspicion of an AE related to the endocrine system.
- g. Pregnancy test will be performed in women of childbearing potential only. A urine or serum pregnancy test is acceptable. Women of childbearing potential are required to have a pregnancy test within 7 days prior to the first dose of study drug and then every 4 weeks. Pregnancy test may occur on Day 1, but results must be available and reviewed by the treating physician or Investigator prior to commencing an infusion.
- h. Results for liver function tests, electrolytes, full blood count, and creatininemust be available before commencing an infusion (samples taken within 3 days prior to infusion) and reviewed by the treating physician or Investigator prior to dosing.
- i. Durvalumab will be administered first, followed by the etoposide + cisplatin/carboplatin regimen.
- j. If cisplatin, infuse over 1 to 2 hours. If carboplatin, infuse over 0.5 to 1 hour.
- k. Chemotherapy regimen (etoposide plus either cisplatin or carboplatin) to be administered Q3W for 4 to 6 cycles, per investigator clinical decision.
- l. See protocol Section 6.1 and Appendix C for additional details relevant to image acquisition, RECIST 1.1 assessments, and evaluation of scans after RECIST 1.1-defined progression.
- m. Patients will have scans done Q6W for the first 12 weeks, and then Q8W thereafter or per institutional standard at investigator discretion.

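### Subgroups by EP cycles received and by PCI use are post-baseline, so PFS and OS comparisons timed from first dose are open to immortal-time bias

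*SAP*

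**What the plan says.** SAP Section 4.2.8 makes subgroup analysis by baseline PS firm and then adds an optional list: "Additional subgroup analyses may be conducted for primary and/or secondary endpoints based on the following". Two entries are "Number of cycles of EP (≤4 versus >4, based on etoposide exposure" and "Use of PCI (yes versus no". For time-to-event analyses a size condition applies: "each subgroup must have at least 20 events per subgroup level in order for that subgroup level to be included in the subgroup analysis".

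The time origins are set in Sections 3.2.3 and 3.2.7: "PFS is defined as the time from first dose of study treatment until the date of objective disease progression or death" and "Overall survival is defined as the time from the date of first dose of study treatment until death due to any cause". APF12 (3.2.4) and OS12 (3.2.8) are the Kaplan-Meier values of these curves at 12 months, so they share the same origin.

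The number of cycles is not fixed in advance. A footnote in Appendix A reads "Chemotherapy regimen (etoposide plus either cisplatin or carboplatin) to be administered Q3W for 4 to 6 cycles, per investigator clinical decision", and the schedule there puts the chemotherapy visits after Day 1 at "Week 3, 6, 9; Weeks 12, 15 at investigator discretion". Section 4.2.2.6 identifies PCI from concurrent or subsequent radiotherapy, so it falls after first dose, and gives no date window. Section 1.2 leaves PCI to the investigator.

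**The concern.** A patient is placed in the >4 group only by being alive and still on etoposide at the fifth cycle, and in the PCI group only by being alive when PCI is given. The time before that point is event-free by definition, yet it is credited to the group. Deaths and stops before Week 12 all go to ≤4, and deaths before PCI all go to no PCI. Kaplan-Meier curves from first dose will then separate with no effect of either factor.

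Other entries in the list show that the authors could anchor a factor: PS is taken at baseline and platinum is fixed to cycle 1. These two factors have no such anchor, and Section 4.2.8 names no landmark, time-dependent covariate or caution. At stake is a prespecified table that could be read as evidence that more chemotherapy or PCI prolongs survival.

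The list also covers the primary endpoints. There the difficulty is separate: the groups differ in exposure and time at risk, and a grade ≥3 AE or imAE that stops EP itself moves the patient into ≤4.

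**Working it through.** **The plan's own figures.** The SAP gives no figure for these subgroups. Its only sample-size figures, the Clopper-Pearson half-widths in Table 1, do reproduce: N=300 gives 4.68, 5.69, 5.80, 5.69 and 5.33% against the stated 4.7, 5.7, 5.8, 5.7 and 5.3%. They do not bear on the size of this bias.

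**Inputs from the SAP.** Fifth cycle no earlier than Week 12 = 84 days; 84/30.4375 = 2.76 months. PFS and OS from first dose. About 300 patients. 20 events per subgroup level.

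**Assumptions, none in the SAP.** Exponential PFS with median 4–12 months; exponential post-progression survival with median 5–8 months; EP stops at progression; 10–90% of patients intended for >4 cycles; 5–30% selected for PCI, given at months 3–6. Neither factor affects outcome.

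**Step 1: one case by hand.** Median PFS 5 months, half intended for >4 cycles.
- Share reaching >4: 0.5 × 2^(−2.76/5) = 0.5 × 0.682 = 0.341.
- APF12, all patients: 2^(−12/5) = 18.9%.
- APF12, >4 group: 2^(−(12−2.76)/5) = 27.8%.
- APF12, ≤4 group: (0.1895 − 0.341 × 0.278)/(1 − 0.341) = 14.4%.

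So APF12 is 27.8% against 14.4% with no effect at all. Simulation of the same case gives the same two values, a PFS hazard ratio of 0.56 and, with median post-progression survival of 8 months, OS12 of 73.6% against 57.3% and an OS hazard ratio of 0.69.

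**Step 2: range over the assumptions** (200,000 simulated patients per scenario, Cox model censored at 24 months, true hazard ratio 1).

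| Comparison | PFS HR | OS HR |
|---|---|---|
| >4 vs ≤4 cycles, 30–70% intended for >4 | 0.41–0.76 | 0.58–0.75 |
| >4 vs ≤4 cycles, 10–90% intended for >4 | 0.22–0.80 | 0.41–0.79 |
| PCI vs none, PCI only while progression-free | 0.45–0.70 | 0.56–0.69 |
| PCI vs none, PCI at any time while alive | 0.89–0.94 | 0.83–0.92 |

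**Step 3: the 20-event rule.** If 5–10% are selected for PCI while progression-free, the PCI group has about 4–10 PFS events by 12 months among 300 patients, below the threshold at that time. In the case of Step 1 the >4 group has 0.341 × 300 ≈ 102 patients and 102 × (1 − 0.278) ≈ 74 events by 12 months, well above it.

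**Step 4: does a landmark remove it?** Restricting to patients still progression-free at Week 12 (cycles, grouped by intended number) or month 6 (PCI), and timing from there, returns hazard ratios of 0.99–1.01 for PFS and 0.98–1.01 for OS.

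**Step 5: patients lost at a landmark.** Week 18, after the last scheduled EP cycle at Week 15, is 126/30.4375 = 4.14 months. The share with a PFS event by then is 1 − 2^(−4.14/7) = 34% at a median of 7 months, 38% at 6 and 44% at 5.

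**The case against.** The strongest reply is that these analyses are optional and descriptive. The list says they may be done, the endpoint is left open, Section 4.1.3 requires no test for the primary endpoints, and no hazard ratio or between-group comparison is described. The 20-event rule could remove a small PCI group. All of that is correct and limits the weight of the point. It does not cure it. Separate medians, APF12 and OS12 set side by side mislead without a p-value, and the event rule addresses precision, not bias.

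A reader might go further and infer that large spurious differences are certain. The SAP does not support that: it states no survival, cycle split or PCI uptake, and the PCI result runs from modest to large.

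A reader might also infer that anyone who progresses or stops early falls into no PCI by construction. That is not so. Section 4.2.2.6 counts subsequent PCI, and Section 3.3.10 defines subsequent anti-cancer therapy as starting after the last dose of study drug. Only death before PCI excludes a patient by construction.

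Nor does immortal time from first dose describe every endpoint. DoR starts at first response and ORR is a proportion. For AE incidence the direction is not clear: longer chemotherapy raises exposure in >4, toxicity stops move patients into ≤4, and ≤4 also holds patients who completed a permitted four-cycle course.

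**Conclusion.** The point holds for PFS, OS, APF12 and OS12. Run as written, subgroup analyses by EP cycles received and by PCI use are open to immortal-time bias towards >4 cycles and towards PCI, and nothing in the SAP corrects it.

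The size rests on inputs outside the document. Under the stated assumptions the cycle comparison is distorted in every scenario tried, although the amount varies widely. The PCI comparison depends mainly on when PCI is given and whether PCI after progression counts. The cycle figures for PFS also assume that EP stops at progression; for OS, survival to Week 12 is guaranteed in the >4 group regardless.

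For AE incidence the two factors are unsuitable for a different reason, unequal exposure and reverse causation, and no size is claimed. The issue does not touch the overall estimates or the baseline PS subgroups. It is worth correcting before analysis because the correction is cheap.

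**What to change.** The simplest change is to delete both factors from the list in Section 4.2.8.

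If they are kept, limit them to PFS and OS with their 12-month rates, and specify one of these:

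- **Landmark analysis.** Include patients still at risk at a stated landmark, group them by status at that time, and measure from the landmark. Week 18 would suit the cycle count, since it follows the last scheduled EP cycle; PCI needs its own stated week. For OS, say whether at risk means alive, or alive and progression-free; the check above used the latter. Apply the 20-event rule to events after the landmark.
- **Time-dependent covariate.** Patients move from ≤4 to >4, or from no PCI to PCI, on the date it happens. This uses everyone, but does not by itself give a 12-month rate per group.

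Do not use either factor for AE incidence, and do not time AEs from the landmark: starting at Week 18 would discard the AEs of the chemotherapy phase, and so much of the grade ≥3 AE primary endpoint.

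The cost is SAP wording and modest programming, with no change to trial conduct. The statistical price of a Week 18 landmark is the loss of roughly 34–44% of patients for PFS (Step 5). Neither method removes confounding, because investigators choose both the number of cycles and PCI, so label the results exploratory.
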